16.22 Definitions and analyses of secondary clinical endpoints

- Safety profile of lenvatinib
- Duration of tumor response
- Progression-free survival time
- Overall survival time
- Patient reported quality of life (QOL) using EQ-5D, and FACT-G

16.221 Safety profile of lenvatinib

All adverse events will be graded using the NCI CTCAE Version 4.0. For each type of adverse event classified as either possibly, probably, or definitely related to study treatment, the proportion of patients experiencing a severe (grade 3 or higher) adverse event will be noted per cycle. The maximum grade for each type of adverse event will be recorded for each patient, and frequency tables will be reviewed to determine adverse event patterns.

16.222 Time to event distributions

Time to event distributions will be estimated using the Kaplan-Meier method

16.2221 Duration of response

Duration of response is defined for all patients whose tumor met the criteria of CR or PR (using the RECIST criteria) as the date at which the patient's objective status is first noted

to be either a CR or PR to the date progression is documented.

16.2223 Progression-free survival

Progression-free survival is defined as the time from registration to documentation of disease progression. If a patient dies without a documentation of disease progression, the patient will be considered to have had tumor progression at the time of their death unless there is sufficient documented evidence to conclude no progression occurred prior to death.

If the patient is declared to be a major treatment violation, the patient will be censored on the date the treatment violation was declared to have occurred. In the case of a patient starting treatment and then never returning for any evaluations, the patient will be censored for progression on Day 1 post treatment.

16.2224 Overall survival time

Overall survival time is defined as the time from registration to death due to any cause.

16.2225 Patient reported quality of life (QOL) using EQ-5D, and/or FACT-G

Descriptive statistics, and scatter plots will form the basis of presentation of these data both overall and by other outcomes (toxicity, response and survival measures). Correlations between the QOL outcomes and other outcome measures will be carried out by standard parametric and non-parametric tests (e.g. Pearson's and Spearman's rho). Comparison between continuous variables will be made with Wilcoxon rank sum tests, Fisher's exact tests will be used to determine differences between categorical variables, and Log-rank test will be used to test differences between time-to-event outcomes.

16.23 Correlative aims:

16.231 For patients with secretory tumors

To examine changes in urinary catecholamine and metanephrine levels during treatment, time series plots of urinary catecholamines and metanephries levels will be constructed (with patient whose tumor responded to treatment in red and patients whose tumor remained stable or progressed in blue) to visually assess trends prior to treatment discontinuation within and between chemistries as well as difference in trends between those whose tumor responded to treatment and those whose tumor did not.

To examine whether lenvatinib-induced changes in urinary catecholamine and/or metanephrine levels during the first cycle of treatment may be associated with objective tumor response, the fold change from baseline levels for each biomarker will be determined. For each biomarker, a plot of the fold change versus response status will be constructed to visually assess differences between those whose tumor

responded to treatment and those whose tumor did not. If feasible, Wilcoxon rank sum tests will be used to examine whether fold changes in a given biomarker during the first cycle of treatment differs between those whose tumor responded to treatment and those whose tumor did not.

- 16.232 To examine associations between tumor response and somatic mutational status in archived tumors, or germline mutational status in patient's peripheral blood mononuclear cells, (presence of SDHD, SDHB, RET, VHL, neurofibromatosis type-1).
For SDHD, SDHB, RET, VHL, neurofibromatosis type-1, a 95% confidence interval for the difference in proportion of patients who have a documented tumor response among those with that particular biomarker present and proportion of patients who have a documented tumor response among those without that particular biomarker present.

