2.2 Secondary objectives

- 2.21 To determine progression-free survival (PFS)
- 2.22 To determine overall survival (OS)
- 2.23 To determine duration of tumor response
- 2.24 To determine safety and tolerability of lenvatinib
- 2.25 To assess patient reported quality of life using EQ-5D-5L and FACT-G

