3.0 ELIGIBILITY

3.1 Inclusion Criteria

- 3.11 Age \geq 18 years.
- 3.12 Histologically or cytologically confirmed malignant secretory or non-secretory pheochromocytoma or paraganglioma that is unresectable and deemed inappropriate for alternative local regional therapeutic approaches.
- 3.13 Measurable disease as defined in [Section 11.0](#).
- 3.14 ECOG Performance Status (PS) 0, 1, or 2 ([Appendix I](#)).
- 3.15 Life expectancy $>$ 24 weeks.
- 3.16 The following laboratory values obtained \leq 14 days prior to registration.
- Absolute neutrophil count (ANC) \geq 1500/mm³
 - White blood cell (WBC) count \geq 3,000/mm³
 - Platelet count \geq 100,000/mm³
 - Hemoglobin \geq 9.0 g/dL (5.6mmol/L)
NOTE: Transfusions are not allowed \leq 7 days prior to registration
 - Total bilirubin \leq 1.5 X upper limit of normal (ULN)
(or total bilirubin \leq 3.0 X ULN with direct bilirubin \leq 1.5 X ULN in patients with well-documented Gilbert's Syndrome)
 - Aspartate transaminase (AST/SGOT) \leq 2.5 X ULN
 - Creatinine \leq 1.5 X ULN
 - Urine protein/creatinine ratio \leq 1 OR 24-hour urine protein $<$ 1.5 gram
- 3.17 Negative pregnancy test done \leq 7 days prior to registration, for women of childbearing potential only.
- 3.18 Blood pressure (BP) $<$ 150 mmHg (systolic) and $<$ 90 mmHg (diastolic). Initiation or adjustment of BP medication is permitted prior to registration provided that the average of three BP readings at a visit prior to registration is $<$ 150/90 mmHg.
- NOTE:** All patients with secretory pheochromocytoma or paraganglioma are REQUIRED to: 1) be evaluated in consultation by a hypertension specialist with specific experience in the management of hypertension in the setting of catecholamine-secreting tumors (usually an endocrinologist, nephrologist, or a cardiologist), and in the setting of hormone-associated hypertension) receive α - and β -adrenergic blockade for at least 7-14 days prior to initiation of lenvatinib (see [Appendix IV](#) for guidelines regarding proper α - and β -blockade). The hypertension specialist of record for each patient should be committed to closely following the patient during the clinical study with evaluation by said specialist required at Cycle 1 and 2 and thereafter on an as needed basis. Please see [Appendix IV](#) for guidelines on hypertension evaluation, follow up and management.
- Please note that this is a critical patient safety issue and that no exceptions to this approach are permitted.**

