9.72 Hypertension

Hypertension is an important AE associated with lenvatinib (Schlumberger, Tahara et al. 2015). Frequent blood pressure (BP) monitoring is important in subjects receiving lenvatinib. In addition patients with secretory pheochromocytomas and paragangliomas are at risk for hypertension and hypertensive crisis by virtue of disease. Patients will be provided with a diary in which to record their daily BP readings (see [Appendix VI](#)) for first three cycles. Daily readings should be taken. If the systolic reading is >140 mmHg OR the diastolic reading is >90 mmHg OR any combination of elevated systolic and diastolic readings, patients will be instructed to retake their blood pressure within 1-4 hours. If a second consecutive reading is elevated patient will be instructed to contact their physician as soon as possible. Patients should seek medical advice if their BP exceeds 180 mmHg (systolic) or 105 mmHg (diastolic) at any time and should also be encouraged to contact their physician if they are concerned about any symptoms that may be associated with high BP (e.g., headache). In addition, expert consultation and follow-up for patients with secretory tumors will be required prior to enrollment, and during the study. Experience to date suggests that increases in BP may occur following dosing with lenvatinib for a number of weeks and that these increases may occur relatively quickly. It is imperative that the investigator institute appropriate measures to control BP. This may necessitate changes to existing antihypertensive medication, addition of new medication(s) and/or holding therapy with lenvatinib. Considering the potential of this adverse event we will monitor patients closely in the initial weeks with frequent measurement of blood pressure in clinic on Day 1, 3 and 10.

Recommendations for hypertension monitoring and management are presented in [Appendix IV](#).

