10.6 Required Routine Reporting

10.61 Baseline and Adverse Events Evaluations

Pretreatment symptoms/conditions to be graded at baseline and adverse events to be graded at each evaluation.

Grading is per CTCAE v4.0 **unless** alternate grading is indicated in the table below:

System Organ Class (SOC)	Adverse event/Symptoms	Baseline	Each evaluation
Blood and lymphatic system disorders	Anemia	X	X
Gastrointestinal disorders	No. of stools	X	
	Diarrhea		X
	Mucositis oral		X
	Nausea	X	X
	Oral dysesthesia		X
	Vomiting		X
	Weight loss		X
General disorders and administration site conditions	Fatigue	X	X
Renal and urinary disorders	Proteinuria	X	X
Respiratory, thoracic and mediastinal disorders	Cough	X	X
Skin and subcutaneous disorders	Rash maculo-papular	X	X
	Palmar-plantar erythrodysesthesia syndrome	X	X
Vascular disorders	Hypertension	X	X

10.62 Submit via appropriate MCCC Case Report Forms (i.e., paper or electronic, as applicable) the following AEs experienced by a patient and not specified in Section 10.6:

10.621 Grade 2 AEs deemed *possibly, probably, or definitely* related to the study treatment or procedure.

10.622 Grade 3 and 4 AEs regardless of attribution to the study treatment or procedure.

10.623 Grade 5 AEs (Deaths)

10.6231 Any death within 30 days of the patient’s last study treatment or procedure regardless of attribution to the study treatment or procedure.

10.6232 Any death more than 30 days after the patient's last study treatment or procedure that is felt to be at least possibly treatment related must also be submitted as a Grade 5 AE, with a CTCAE type and attribution assigned.

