For α -adrenergic blockade phenoxybenzamine is the preferred drug. The initial dosage is 10 mg once or twice daily, and the dose is increased by 10 to 20 mg in divided doses every 2 to 3 days as needed to control blood pressure. The final dosage of phenoxybenzamine is typically between 20 and 100 mg daily. The patient should be warned about the orthostasis, nasal stuffiness, and fatigue that occur in almost all patients. With their more favorable side-effect profiles and cost-effectiveness, selective α_1 -adrenergic blocking agents (e.g., prazosin, terazosin, or doxazosin) may be used for those patients who are intolerant of the side effects of phenoxybenzamine or cannot afford phenoxybenzamine. Ultimately, the choice of the agents is at the discretion of the hypertension specialist.

The β -adrenergic antagonist should be administered only after α -adrenergic blockade is effective (with near-normal BP) because with β -adrenergic blockade alone hypertension may be more severe from the unopposed α -adrenergic stimulation. β -adrenergic blockade is indicated to control the tachycardia associated with both the high concentrations of circulating catecholamines and the α -adrenergic blockade. The clinician should exercise caution if the patient is asthmatic or has congestive heart failure. Chronic catecholamine excess can produce a myocardiopathy that may become evident with the initiation of β -adrenergic blockade, resulting in acute pulmonary edema. Therefore, when the β -adrenergic blocker is administered, it should be used cautiously and at a low dose. For example, a patient is usually given 10 mg of propranolol every 6 hours to start. On the second day of treatment, the β -adrenergic blockade (assuming the patient tolerates the drug) is converted to a single long-acting dose of a

cardioselective β -blocker. The dose is then increased as necessary to control the tachycardia (goal heart rate is 60-80 beats per minute).

Metyrosine, a catecholamine synthesis inhibitor, may be used in patients with particularly high metanephrenes/normetanephrenes and/or for difficult to control hypertension prior to initiation of lenvatinib. Typical doses may be up to 1-2 grams per day, but dose escalation is often limited by sedation.

Metyrosine may also be used if there is significant concern for lenvatinib-induced catecholamine release following initiation of therapy.

Orally Administered Drugs for Initial α - and β -Adrenergic Blockade

Drug	Dosage, mg/day*	Side effects

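### Section 16.221 defines its Grade 3+ proportion on treatment-related events only, and its maximum-grade tables state no attribution scope and ignore baseline grade

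*Combined protocol and SAP*

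**What the plan says.** The safety objective in 2.2 is "To determine safety and tolerability of lenvatinib". Section 16.221 serves it with two summaries.

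- The first begins "For each type of adverse event classified as either possibly, probably, or definitely related to study treatment, the proportion of patients experiencing a severe". The sentence goes on to define severe as Grade 3 or higher and to say that the proportion is noted per cycle.
- The second reads "The maximum grade for each type of adverse event will be recorded for each patient, and frequency tables will be reviewed". It states neither an attribution scope nor a baseline reference.

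Section 16.31 makes patients evaluable for adverse events from first dose but does not define a treatment-emergent event.

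Data collection is broader than the analysis text. Section 10.61 asks for "Pretreatment symptoms/conditions to be graded at baseline and adverse events to be graded at each evaluation", and its table marks both hypertension and fatigue at both times. For events outside that table, 10.622 requires "Grade 3 and 4 AEs regardless of attribution to the study treatment or procedure".

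The protocol also names competing causes. Section 9.72 says that "patients with secretory pheochromocytomas and paragangliomas are at risk for hypertension and hypertensive crisis by virtue of disease". Appendix IV, D.3, makes phenoxybenzamine the preferred alpha-blocker and lists among its effects "fatigue that occur in almost all patients". Blockade is required for secretory tumors only (3.18 and Appendix IV, D2).

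**The concern.** Under the categories in 10.3, an event judged unlikely or unrelated drops out of the only Grade 3+ proportion that the plan defines. With one arm, nothing in the data shows whether that judgement was right. This matters most for hypertension in secretory patients, where drug and disease can both be the cause. Section 1.3 gives that overlap as the reason for the reduced starting dose, and 9.5 expects worsening, especially with secretory tumors.

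Other safety provisions do not fill the gap. The stopping rule in 16.41 counts related events only and excepts hypertension from its non-hematologic criterion. Section 10.31 exempts hypertension up to Grade 3 from expedited reporting unless it leads to hospitalization. Section 16.221 is therefore the main planned summary of severe hypertension.

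The maximum-grade tables have a different weakness. Without a baseline reference, a condition that was present at entry and never changed is tabulated as an on-study maximum.

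**Working it through.** **The plan's own figure.** There is none to reproduce. The operating characteristics in 16.13 concern tumor response, and the plan gives no target rate or precision for safety.

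**Attribution: inputs.** The documents give 42% Grade 3+ hypertension on lenvatinib in a thyroid cancer trial (1.233) and a maximum of 23 eligible patients (16.122). They give no background rate and no accuracy of attribution, so both are assumed:

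- q = 42%, treated as the rate caused by lenvatinib;
- b = rate from other causes, assumed 5% to 30% and independent of q;
- m = share of background events called related, 0 to 1;
- s = share of lenvatinib-caused events called related, first 1, then 0.8.

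**Formulas.** All-cause rate = 1 − (1 − q)(1 − b). Related-only rate = 1 − (1 − qs)(1 − bm).

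With s = 1:

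| b | All-cause = 1 − 0.58 × (1 − b) | Related-only, m = 0 to m = 1 | Largest gap | Gap × 23 patients |
|---|---|---|---|---|
| 5% | 44.9% | 42.0% to 44.9% | 2.9 points | 0.7 |
| 10% | 47.8% | 42.0% to 47.8% | 5.8 points | 1.3 |
| 20% | 53.6% | 42.0% to 53.6% | 11.6 points | 2.7 |
| 30% | 59.4% | 42.0% to 59.4% | 17.4 points | 4.0 |

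With s = 0.8 and m = 0, the related-only rate is 0.42 × 0.8 = 33.6%. With s = 0.8 and m = 1, it is 1 − 0.664 × 0.90 = 40.2% at b = 10%, and 1 − 0.664 × 0.80 = 46.9% at b = 20%. Against the assumed drug-caused 42%, the related-only rate can thus fall on either side. Against the all-cause rate, it can only be equal or lower.

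For Grade 3+ fatigue, with both rates assumed (q = 10%, b = 20%, s = 1), the related-only rate runs from 10% to 28% and the all-cause rate is 28%.

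For scale, 10 of 23 patients (43.5%) has an exact 95% interval of 23.2% to 65.5%.

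**Baseline: blood pressure.** Section 3.18 allows entry when "the average of three BP readings at a visit prior to registration is" below 150/90 mmHg. Appendix IV puts Grade 2 at systolic 140–159 and Grade 3 at systolic 160 or diastolic 100 and above. A patient entering at systolic 140–149 is therefore already Grade 2 by those cut-offs and would show Grade 2 as the on-study maximum with no change. No patient who meets the entry limit is at Grade 3 by them.

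**Baseline: timing.** Under 4.1 the pretreatment adverse event assessment may fall up to 14 days before registration, and under 6.6 treatment may start up to 14 days after it: 14 + 14 = 28 days. Blockade must precede lenvatinib by at least 7–14 days, so it can begin after the baseline grading. Fatigue from blockade would then look new on study. Section 4.1 also schedules an adverse event assessment on Day 1 of Cycle 1, which could serve as the reference if taken before the dose.

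**What the collected data allow.** Events listed in 10.61 are graded at each evaluation with no attribution limit. Other events are collected regardless of attribution at Grade 3 and 4 (10.622) and, for deaths, within 30 days of last treatment (10.6231). Other Grade 2 events are collected only if judged related (10.621). An all-cause table is therefore possible at every grade for the 10.61 list, but only from Grade 3 for the rest.

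**The case against.** The strongest reply is that the related-only filter is attached to a per-cycle figure, while the whole-study, per-patient summary is the maximum-grade table, which carries no such limit and may already contain all-cause Grade 3+ counts. This stands in part: a reader might infer that the plan counts related events throughout, and the text does not say so. But it does not say that the tables are all-cause either.

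Second, a reader might infer that the severe hypertension rate is biased low by a definite amount. The documents do not support that. Being possibly related is enough to keep an event in, the protocol itself treats hypertension as a known lenvatinib effect, and nothing indicates what share of severe events would be called unrelated. Sampling error of about 20 points either way also exceeds every gap in the table. This stands as to size. A larger sample would not remove the dependence on attribution, however.

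Third, if the question is what lenvatinib adds, an all-cause rate is too high by the background contribution. This stands, and it governs how the all-cause rate should be described.

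Fourth, the baseline argument is weak for severe hypertension, since entry limits exclude Grade 3 blood pressure by the Appendix IV cut-offs. This stands. Appendix IV also says that adverse event grading follows standard CTCAE, whose text is not in the documents.

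Finally, disease and blockade should not be merged. The disease is named as a cause of hypertension and phenoxybenzamine as a cause of fatigue, with no grade stated. Blockade is given to normalize blood pressure.

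**Conclusion.** The point holds as a gap in the analysis text. The only defined Grade 3+ proportion depends on an attribution that a single-arm trial cannot verify. The maximum-grade tables have no stated scope and count pre-existing conditions as on-study findings.

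The size of the attribution effect is unknown. The range of 0 to 17.4 points below the all-cause rate (0 to 4.0 of 23 patients) rests on an assumed background of 5% to 30%, a 42% rate borrowed from another population, independence of the two causes, and every lenvatinib-caused event being called related. The baseline effect falls mainly on lower-grade hypertension and on fatigue.

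It would be tempting to conclude that the trial cannot give a sound safety rate. The documents do not support that: baseline grades and all Grade 3–4 events are collected, so sound descriptive rates can be produced. Safety is a descriptive secondary objective with no threshold, and no decision rule depends on these tables. The change is worth making because the better summaries need no new data.

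**What to change.** Amend 16.221 as follows.

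- Report the per-patient Grade 3+ proportion regardless of attribution, alongside the related-only proportion. Describe the all-cause rate as an incidence, not as the effect of lenvatinib.
- State that the maximum-grade tables are all-cause. For events outside the 10.61 list, note that this is complete only from Grade 3.
- For events graded at baseline in 10.61, count an event as treatment-emergent only if it is new or worse than the last pre-dose grade, using the Day 1 assessment where one was made before the dose.
- Give baseline-to-worst-grade shift tables for those events.
- Show hypertension and fatigue separately for secretory and non-secretory tumors (factor 12.6).

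The cost is SAP wording and a few extra tables, with no additional patients or data items. The severe-event rates may look less favourable, and the subgroup counts will be small.

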In the SELECT phase 3 trial (Schlumberger, Tahara et al. 2015), hypertension was most common observed adverse effect. It was seen in 68% of the enrolled subjects and grade ≥ 3 hypertension was seen in 42%. Other common adverse effects included fatigue (59%), diarrhea (59%), decreased appetite (50%), decreased weight (46%), nausea

(41%), stomatitis (36%), palmo-plantar erythrodysesthesia (32%) and proteinuria (31%). With the limited experience of using lenvatinib in paraganglioma/pheochromocytoma patients, we postulate that some patients may experience profound and quick response to therapy that may result in mild tumor lysis-like syndrome (Jasim Sina 2016).

1.234 Quality -of -Life (QOL) Measurements for use of Lenvatinib

As described above kinase inhibitors have been used previously for the treatment of advanced paraganglioma and pheochromocytoma patients (Ayala-Ramirez, Chougnat et al. 2012). Ayala-Ramirez et al. have described the largest cohort of patients treated with sunitinib for advanced and progressive metastatic pheochromocytoma/ and paraganglioma, however, data on QOL was unfortunately missing

Clinical efficacy data on lenvatinib are derived from phase III, randomized, double-blind, multicenter study involving patients with progressive thyroid cancer that was refractory to iodine-131 (SELECT study) described above (Schlumberger, Tahara et al. 2015). This study, however, lacked the data on patient reported QOL during and after therapy.

Data on QOL with other kinase inhibitors are variable. For instance, there was no reported change in QOL in renal cell carcinoma treated with sorafenib (Bukowski, Cella et al. 2007). While mild but detectable impact on health-related quality of life was noticed in patients with thyroid cancer (Schlumberger 2013).

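### The maximum-grade adverse event tables in 16.221 cover every event type, but 10.62 does not routinely collect low-grade events outside the 10.61 list, so any-grade frequencies for those terms are biased downward

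*Combined protocol and SAP*

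**What the plan says.** **Analysis.** Section 16.221 is the only analysis text for the safety and tolerability objective (2.24). It opens with "All adverse events will be graded using the NCI CTCAE Version 4.0". For treatment-related events it then plans a severe-event rate: "the proportion of patients experiencing a severe (grade 3 or higher) adverse event will be noted per cycle". The last element is the table at issue: "The maximum grade for each type of adverse event will be recorded for each patient", followed by a review of frequency tables. Neither a minimum grade nor a restriction to particular terms is given.

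**Collection.** Section 10.61 is headed by the instruction "Pretreatment symptoms/conditions to be graded at baseline and adverse events to be graded at each evaluation" and marks 13 terms for grading at each evaluation. Section 10.62 then governs "the following AEs experienced by a patient and not specified in Section 10.6". For these it requires submission of:

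- Grade 2 events judged possibly, probably or definitely related (10.621);
- "Grade 3 and 4 AEs regardless of attribution to the study treatment or procedure" (10.622);
- deaths as defined in 10.623.

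Section 10.1, item f, adds that anything reported by an expedited route must also be reported routinely. Under the table in 10.41, a Grade 1 or 2 serious event qualifies for that route when it leads to hospitalization of at least 24 hours.

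**The concern.** The analysis section asks for more than the collection section delivers. For a listed term, the absence of a record means that the term was assessed and no event was graded. For an unlisted term, it may mean no event, a Grade 1 event, or a Grade 2 event judged unrelated. Placing both kinds of term in one maximum-grade table mixes two floors without saying so, and for unlisted terms the error runs in one direction only.

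What is at stake is the description of tolerability at the 20 mg starting dose. The rates in 1.233 are the obvious yardstick for a reader of the results, and low-grade decreased appetite would look rarer than it is beside them. Section 16.2225 also plans to relate quality of life to toxicity, so incomplete low-grade data could carry over into that analysis.

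**Working it through.** The plan states no figure on this point. The check sets the sections side by side and then illustrates the direction of the bias.

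**Step 1. What reaches the case report form routinely**

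| Event | Term listed in 10.61 | Term not listed |
|---|---|---|
| Grade 1 | yes | no |
| Grade 2, unrelated | yes | no |
| Grade 2, at least possibly related | yes | yes (10.621) |
| Grade 3 or 4 | yes | yes (10.622) |
| Grade 5 | yes | as defined in 10.623 |

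The two cells marked no have one exception, events reported by expedited means.

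**Step 2. Which terms are listed.** The 13 terms marked for each evaluation are anemia, diarrhea, oral mucositis, nausea, oral dysesthesia, vomiting, weight loss, fatigue, proteinuria, cough, maculo-papular rash, palmar-plantar erythrodysesthesia and hypertension.

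**Step 3. Compare with the toxicities that the protocol names as common.**

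- Section 1.233 quotes nine from the phase 3 trial. Eight have a listed counterpart: hypertension 68%, fatigue 59%, diarrhea 59%, weight decrease 46%, nausea 41%, stomatitis 36% (oral mucositis), palmar-plantar erythrodysesthesia 32% and proteinuria 31%. Decreased appetite, 50%, has none.
- Section 15.17 puts nine terms in its list of toxicities above 10%. Diarrhea, nausea, vomiting and hypertension are listed in 10.61. Abdominal pain, asthenia, decreased appetite, dehydration and acute kidney injury are not. Dehydration also appears in the 1%-10% list of the same section.

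**Step 4. Illustration for decreased appetite.** Inputs: the 50% rate (1.233), assumed to carry over to this population and dose; N = 23 eligible patients or 25 in total (16.122); and g, the share of affected patients whose maximum grade falls below the 10.62 floor. The documents do not give g, so it is an assumption and may lie anywhere from 0 to 100%.

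Expected patients affected = 0.50 × N = 11.5 of 23, or 12.5 of 25. Expected patients recorded = 0.50 × N × (1 − g):

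| g (assumed) | Recorded, N = 23 | Recorded, N = 25 | Apparent rate |
|---|---|---|---|
| 0% | 11.5 | 12.5 | 50% |
| 20% | 9.2 | 10.0 | 40% |
| 40% | 6.9 | 7.5 | 30% |
| 60% | 4.6 | 5.0 | 20% |
| 80% | 2.3 | 2.5 | 10% |
| 100% | 0 | 0 | 0% |

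The table ignores low-grade events rescued by expedited reporting, whose number cannot be derived from the documents. It shows direction and possible range; it is not an estimate.

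**Step 5. What is not affected.** The severe-event rate in 16.221 uses related events of Grade 3 or higher, and the stopping rule in 16.41 uses related events of Grade 4 or higher. Both lie above the collection floor for every term.

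**The case against.** The strongest reply is that a two-tier floor is openly specified in 10.61 and 10.62, and that the choice of terms to solicit is a matter of judgement. The list covers eight of the nine common toxicities in 1.233, so it is far from arbitrary. No comparison with the phase 3 rates is planned, and no decision rule uses low-grade counts. Weight loss is collected at all grades, and the FACT-G asks about pain and about being bothered by side effects. All of this stands and limits the weight of the point. It does not close the gap: 16.221 still describes a table without a floor, and the FACT-G in Appendix VII has no appetite item. Suppose the relatedness condition attached to the severe-event rate were read into the maximum-grade table as well. Unrelated Grade 2 events would then fall outside it, but related Grade 1 events would still be missing.

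Three stronger readings are tempting, and the documents do not support them.

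- A reader might infer that uncollected events are entered as no event. No section says how a blank is coded or displayed, and 18.1 refers submission instructions to a schedule held in the data capture system, which is not part of the documents. What can be said is that the two situations cannot be distinguished from what 10.62 routinely requires.
- A reader might infer that mild events in general vanish from the tables. They do not: every grade of the 13 listed terms, and related Grade 2 events of any other term, are collected with their grade.
- A reader might infer that the trial's common toxicities as a group will be understated, enough to support a false claim of good tolerability. Eight of the nine in 1.233 are fully collected, so the documents do not carry that conclusion.

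**Conclusion.** The mismatch is real and narrow. Followed as written, the plan gives downward-biased any-grade frequencies for terms outside 10.61, on a different footing from the listed terms. Among the toxicities in 1.233 this touches decreased appetite alone; among those above 10% in 15.17 it also touches abdominal pain, asthenia, dehydration and acute kidney injury. The size cannot be determined, because the grade distribution is not given: for decreased appetite the apparent rate could lie anywhere between 50% and 0%, if the 50% rate applies here at all. The conclusion rests on reading 10.62 as the complete routine requirement for unlisted terms, with expedited reports as the exception. The primary endpoint, the severe-event rates and the stopping rule are untouched. This is a minor point, worth acting on because the correction is cheap.

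**What to change.** 1. In 10.61, add decreased appetite (CTCAE anorexia) and abdominal pain to the terms graded at baseline and at each evaluation. Consider the other unlisted terms above 10% in 15.17: asthenia, dehydration and acute kidney injury.
2. In 16.221, state that any-grade and maximum-grade frequencies are presented only for 10.61 terms. Tabulate all other terms separately, labelled with the floor actually collected: Grade 2 if at least possibly related, and Grade 3 or higher regardless of attribution. Do not cut these terms to Grade 3 or higher only, since that would discard the related Grade 2 events that 10.621 already collects.

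The cost is a sentence or two in 16.221 and a few extra case report form rows, completed at visits where adverse events are already assessed under the test schedule in 4.1. For any patient treated before the change, the added terms would be complete only from the date it takes effect, and the table should say so.
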